### 3.2 Sample Size

It is anticipated that approximately **95** subjects will be enrolled in this study. **For Schedule A**, approximately 40 subjects will be enrolled in the dose escalation cohorts and up to 10 additional subjects will be enrolled in the dose expansion cohort. **For Schedule B**, up to **40 subjects will be enrolled in the dose escalation cohorts and up to 10 additional subjects will be enrolled in the dose expansion cohort**. For ethical and operational reasons subjects who already are in the screening phase at the time of enrollment stop (end of expansion phase) **may** still be allowed to be treated. Therefore, an over running of subject recruitment might be possible.

Based on emerging data, additional subjects may be enrolled **or a schedule may be discontinued**.

The sample size in the dose escalation is based on practical considerations and is consistent with conventional oncology studies with the objective to estimate the MTD. With 3 subjects per cohort, there is a 27-70% probability of observing at least one DLT if the true DLT rate is 10-33% and with 4 subjects per cohort, there is a 34-80% probability.

In the dose expansion cohort, a subject number of 10 will provide a 65% probability of observing at least one adverse event with 10% incidence rate and 89% probability of observing at least one adverse event with 20% incidence rate. An exact 80% binomial confidence interval (CI) will be provided for overall response rate. With the 10 subjects and 20% overall response rate, the expected 80% CI would be 5.5% to 45.0% with the half-width 19.8%.

## 4. Covariates and Subgroups

### 4.1 Planned Covariates

The relationship of covariates to efficacy endpoints will be explored if appropriate.

## 5. Definitions

### Age at Enrollment

Subject age at enrollment will be collected using the age in years in the clinical database.

### AUC0-last

Area under the concentration-time curve from time 0 (time of investigational product administration) to the time of the last quantifiable concentration.

### Baseline

For any variable, unless otherwise defined, baseline is the last assessment taken prior to the first investigational product administration.

### ECG analysis value

The mean value of triplicate will be calculated and used in the analysis. If an ECG is missing within a triplicate, all available data will be averaged for that timepoint. Further, unscheduled ECG measurements taken up to 5 minutes after the last assessment of a triplicate at a timepoint will be included in the mean for that timepoint.

### Baseline ECG

The baseline ECG is defined as the average of the mean of the triplicates at predose assessments from cycle 1 day 1; the mean of values in a triplicate should be calculated before taking the mean of the triplicate averages.

### Bazett-corrected QT Interval (QTcB)

The Bazett correction will be calculated from the investigator reported QT (msec) and RR interval (msec), as follows:

$$QTcB = QT / (RR/1000)^{1/2}$$

### Change From Baseline

Change from Baseline is the arithmetic difference between post-Baseline and Baseline.

### Cmax

Maximum observed serum concentration.

Cmin

Minimum observed serum concentration

End-of-Study

Primary Completion: The primary completion date is defined as the date when the last subject is assessed or receives an intervention for the purposes of final collection of data for the primary endpoint(s), for the purposes of conducting the primary analysis, whether the study concluded as planned in the protocol or was terminated early.

The primary completion date is the date when the last subject either had the opportunity to receive up to 2 cycles of treatment or terminated the study early.

If the study concludes prior to the primary completion date originally planned in the protocol (ie, early termination of the study), then the primary completion will be the date when the last subject is assessed or receives an intervention for evaluation in the study (ie, last subject last visit).

End of Study: The end of study date is defined as the date when the last subject is assessed or receives an intervention for evaluation in the study (ie, last subject last visit); the final analysis will occur at this time.

Enrollment Date

Enrollment date is defined as the first dose of IP date.

Fridericia-corrected QT Interval (QTcF)

The Fridericia correction will be calculated from the investigator reported QT (msec) and RR interval (msec), as follows:

$$QTcF = QT / (RR/1000)^{1/3}$$

Investigational Product

The term 'investigational product' is used in reference to AMG 673.

Percent Change From Baseline

Percent change from Baseline is the arithmetic difference between post-Baseline and Baseline divided by Baseline values times 100.

Percent change from baseline =  $[(\text{Post-baseline Value} - \text{Baseline Value}) / \text{Baseline Value}] \times 100$

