7.3.8 Electrocardiogram Performed in Triplicate

The subject must be in supine position in a rested and calm state for at least 5 minutes before ECG assessment is conducted. If the subject is unable to be in the supine position, the subject should be in most recumbent position as possible.

Electrocardiograms should be performed in a standardized method, in triplicate, and approximately 30 seconds apart, prior to blood draws or other invasive procedures. Each ECG must include the following measurements: QRS, QT, QTc, RR, and PR intervals.

Electrocardiograms will be performed as follows:

- Three sets of baseline ECGs will be collected ≥ 30 minutes apart, with each baseline ECG in triplicate run consecutively (ie, < 30 seconds apart; 2 sets collected at screening, and 1 set collected pre-dose on day 1 [ie, total ≥ 9 ECGs])
- Triplicate ECGs at time points after dosing

Baseline is defined as predose assessments from cycle 1 day 1. The investigator or designated site physician will review all ECGs. Electrocardiograms will be transferred electronically to an ECG central reader for analysis per Amgen instructions. Once signed, the original ECG tracing will be retained with the subject's source documents. At the request of the sponsor, a copy of the original ECG will be made available to Amgen.

Standard ECG machines should be used for all study-related ECG requirements.

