### 9.6.6 Electrocardiogram

All on-study electrocardiogram (ECG) data will be listed and select parameters of interest may be plotted.

Summaries over time and/or changes from baseline over time will be provided for all ECG parameters.

The analysis of Fridericia's (QTcF) QT correction will use the results recorded on the CRF. Subjects' maximum change from baseline in QT interval corrected by Fridericia's formula will be categorized into the following groups per their maximum change from baseline in QTcF. Unscheduled assessments will be included in the determination of the maximum change.

[figure not shown]
- $\leq 30$  msec
- $>30 - 60$  msec
- $>60$  msec

The number and percentage of subjects in each group will be summarized.

Subjects will also be categorized into the following groups per their maximum post baseline QTcF. Unscheduled assessments will be included in the determination of the maximum post baseline value.

- $\leq 450$  msec
- $>450 - 480$  msec
- $>480 - 500$  msec
- $>500$  msec

The number of subjects in each group will be summarized for each dosing group.

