**13. Data Not Covered by This Plan**

Not Applicable

14. Appendices

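### The SAP takes QTcF from site-reported QT and RR and gives the central ECG readings provided for in the protocol no stated role (minor)

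*SAP*

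**What the plan says.** Protocol 7.3.8 describes two looks at the ECGs. At the site, "The investigator or designated site physician will review all ECGs". Then "Electrocardiograms will be transferred electronically to an ECG central reader for analysis per Amgen instructions". It also specifies the content of each tracing: "Each ECG must include the following measurements: QRS, QT, QTc, RR, and PR intervals".

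The SAP names only the site as the source of QTc. In Section 5 the QTcF entry reads "The Fridericia correction will be calculated from the investigator reported QT (msec) and RR interval (msec), as follows", and the QTcB entry reads "The Bazett correction will be calculated from the investigator reported QT (msec) and RR interval (msec), as follows". Section 9.6.6 adds "The analysis of Fridericia's (QTcF) QT correction will use the results recorded on the CRF". That section then defines two tables: maximum change from baseline (up to 30, above 30 to 60, above 60 msec) and maximum post-baseline value (up to 450, above 450 to 480, above 480 to 500, above 500 msec). Unscheduled assessments count towards both maxima.

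The ECG analysis value in SAP Section 5 is the mean of a triplicate, with no reader named. SAP 8.2 (data transfer) mentions no central ECG data. SAP Section 10 declares one change from the protocol's analyses, and it does not concern ECGs. Protocol 10.4.2 asks for the QTcF categories without naming a reader.

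**The concern.** The protocol arranges a central reading whose stated purpose is analysis, yet the analysis plan draws its QTc values from the other reading. Central reading puts the measurements under one process, whereas the site values come from about 10 sites. That central reading is the more uniform of the two is a methodological judgement; the documents do not say so.

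The source matters because of the form of the tables. A subject is classified by the largest of several readings, so random reading error pushes in one direction: it can move a subject up a category, and the chance of this grows with the number of time points. If site readings carry more error, the tables could show apparent QTcF prolongation that comes from measurement. In a first-in-human trial with small cohorts, one or two such subjects would be visible.

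**Working it through.** **Text comparison.**

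| Question | Protocol | SAP |
|---|---|---|
| Who reads the ECGs? | Site physician and central reader (7.3.8) | Investigator only (Section 5: QTcF, QTcB) |
| Source of the QTcF tables? | Not named (10.4.2) | CRF (9.6.6) |
| Role of the central readings? | Analysis, per sponsor instructions (7.3.8) | None stated |

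The SAP does not contradict the protocol's analysis text, which is silent on the source. The gap is that a reading made for analysis is not assigned to one.

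**Illustration of size.** The plan has no figure to reproduce, and the documents give no reading variability. Everything below rests on assumptions.

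Inputs:
- SD of a change from baseline, σ: 10, 13 and 15 msec. Assumed: 10 stands for a quieter reading process, 13 and 15 for noisier ones.
- No true drug effect; changes normally distributed with mean 0.
- Number of post-dose time points, n: 4 and 10. The schedule tables (Protocol Tables 6 and 7, partly broken in extraction) suggest about four post-dose ECG times in one two-dose Schedule A cycle with end of study, and roughly nine over two cycles.
- Correlation between changes, ρ = 0.5. All changes share one baseline. If baseline and post-dose values each have variance s², a change has variance 2s² and two changes have covariance s², so ρ = s²/2s² = 0.5.

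Single time point, P(change > 30) = 1 − Φ(30/σ):
- σ = 10: 1 − Φ(3.00) = 0.13%
- σ = 13: 1 − Φ(2.31) = 1.05%
- σ = 15: 1 − Φ(2.00) = 2.28%

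Any of n time points, threshold c:

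P(max > c) = 1 − ∫ φ(z) · [Φ((c/σ − √ρ·z)/√(1 − ρ))]ⁿ dz

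| σ (msec) | c = 30, n = 4 | c = 30, n = 10 | c = 60, n = 10 |
|---|---|---|---|
| 10 | 0.5% | 1.1% | < 0.001% |
| 13 | 3.5% | 7.0% | 0.002% |
| 15 | 7.2% | 13.3% | 0.03% |

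Treating the ten changes as independent, 1 − (1 − p)¹⁰, would give 1.3%, 10.0% and 20.6%. That ignores the shared baseline and overstates the effect.

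The effect is therefore confined, under these assumptions, to the boundary at 30 msec. No calculation is offered for the 450, 480 and 500 msec boundaries: it would need the distribution of subjects' true QTcF, which the documents do not give.

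**The case against.** The strongest reply is that the SAP pre-specifies a source openly, that protocol 10.4.2 requires no other, and that preferring central readings is a matter of taste in a descriptive table. Four parts of the case against deserve an answer.

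- **Differences between sites largely cancel.** If a subject's baseline and later ECGs are read at the same site in the same way, a stable site offset drops out of the change. Only variation within a site adds noise. This stands, and it means that the number of sites does not by itself inflate the change table. Averaging over triplicates reduces the noise further.
- **The size is assumed.** This stands. The SDs are not in the documents, and if site readings are as precise as central ones there is no inflation.
- **Every ECG centrally read?** A reader might infer that all ECGs go to the central reader and that the results are already in hand. The documents do not support this. The word all belongs to the site physician's review; the transfer is qualified by sponsor instructions that we cannot see, and nothing says when or whether a transferred tracing is read.
- **Central results never used?** A reader might infer this from the entry under "Data Not Covered by This Plan", which is Not Applicable. That is weak evidence: SAP 9.5 carries the same entry although 9.5.2 goes on to describe efficacy analyses. SAP 9.6.6 also promises a listing of all on-study ECG data, which could include central readings.

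What survives is narrower: the two QTcF tables are tied explicitly to site-reported or CRF values, and no visible SAP text assigns the central readings a role.

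**Conclusion.** The point holds as a minor one. The protocol provides for a central ECG reading for analysis; the SAP builds QTcF, QTcB and the QTcF outlier tables on the site's reading and does not say what the central reading is for. If site readings are the noisier, the likely consequence is some excess in the category for a change above 30 msec, illustrated at up to 7.2% of subjects over 4 time points and 13.3% over 10 under the largest assumed SD, against 0.5% and 1.1% under the smallest. These figures depend on the assumed SDs, normality, ρ = 0.5 and no true effect; they are not estimates for this trial.

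It would be tempting to conclude that the counts above 60 msec, or above 480 and 500 msec, are inflated too. The first is contradicted by the same assumptions (at most 0.03%), and the second has no calculation behind it.

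Severity is minor because the ECG tables are descriptive, no hypothesis is tested on them, and the BLRM is fitted to event incidence, not to QTc.

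**What to change.** In SAP Section 5 (QTcF and QTcB) and 9.6.6, name the central reader's QT and RR as the source for QTcF, change from baseline and both sets of outlier categories wherever a central reading exists. Keep the investigator-reported values for listings and one supportive table.

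Some ECGs may lack a central reading. The SAP should say that the site value is then used and flagged, because a change that combines a central baseline with a site post-dose value brings back the difference between readers.

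The same edit can settle whether QTcF is calculated from QT and RR (Section 5) or taken as recorded (9.6.6), a separate ambiguity that one clear sentence on the source would also resolve.

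Cost: SAP wording and one added data transfer, to be named in SAP 8.2. No change to the conduct of the trial is needed, provided that the sponsor's instructions have the central reader supply QT and RR; this should be confirmed first.

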#### Fold change from Baseline

Fold change from Baseline equals the post-Baseline value divide by the Baseline value.

Fold change from baseline =  $\text{Post-baseline Value} / \text{Baseline Value}$

#### Study Day

Post study day 1:  $\text{study day} = (\text{date} - \text{date of Study Day 1}) + 1$

Pre study day 1:  $\text{study day} = (\text{date} - \text{date of Study Day 1})$

#### Study Day 1

Study day 1 is defined as the first day of administration of the investigational product after enrollment. The day prior to Study Day 1 is considered Day -1.

#### Treatment-Emergent Adverse Event (TEAE)

Treatment-emergent adverse events are events categorized as Adverse Events (AEs) **including disease related events** starting on or after the first dose of investigational product, as determined by the flag indicating if the adverse event started prior to the first dose on the Events CRF and up to end of study (EOS).

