9. SAFETY DATA COLLECTION, RECORDING, AND REPORTING

9.1 Definition of Safety Events

9.1.1 Disease-Related Events

Disease-Related Events are events (serious or non-serious) anticipated to occur in the study population due to the underlying disease (see [Appendix G](#) for a list of expected disease-related events).

The investigator is responsible for ensuring that all disease-related events observed by the investigator or reported by the subject that occur after the first dose of investigational product through the end of study are reported recorded using the Event CRF.

All serious disease-related events will be recorded and reported to the sponsor or designee within 24 hours. The investigator will submit any updated serious disease-related event data to the sponsor within 24 hours of it being available.

Disease-Related Events that do not qualify as Adverse Events or Serious Adverse Events:

- An event which is part of the normal course of disease under study (eg, disease progression in oncology or hospitalization due to disease progression) is to be reported as a Disease-Related Event.
- Death due to the disease under study is to be recorded on the Event CRF.

Approved

Disease-Related Events that would qualify as an Adverse Event or Serious Adverse Event:

- An event based on the underlying disease that is worse than expected as assessed by the investigator for the subject's condition, or if the investigator believes there is a causal relationship between the investigational product(s)/study treatment/protocol-required therapies and disease worsening, this must be reported as an Adverse Event or Serious Adverse Event.

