9.1.3 Serious Adverse Events

A serious adverse event is defined as an adverse event that meets at least 1 of the following serious criteria (unless it meets the definition of a Disease-Related Event as defined in [Section 9.1.1](#)):

- fatal
- life threatening (places the subject at immediate risk of death)
- requires in patient hospitalization or prolongation of existing hospitalization
- results in persistent or significant disability/incapacity
- congenital anomaly/birth defect
- other medically important serious event

A Disease-Related event (eg., related to disease progression) is to be reported as a serious adverse event if:

- the subject's pre-existing condition becomes worse than what the investigator would consider typical for a patient with the same underlying condition, or
- if the investigator believes a causal relationship exists between the investigational medicinal product(s)/protocol-required therapies and the event,
- and the event meets at least 1 of the serious criteria above.

An adverse event would meet the criterion of "requires hospitalization", if the event necessitated an admission to a health care facility (eg, overnight stay).

If an investigator considers an event to be clinically important, but it does not meet any of the serious criteria, the event could be classified as a serious adverse event under the criterion of "other medically important serious event". Examples of such events could include allergic bronchospasm, convulsions, blood dyscrasias, drug induced liver injury (DILI) (see [Appendix A](#) for DILI reporting criteria), or events that necessitate an emergency room visit, outpatient surgery, or urgent intervention.

Approved

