9.2 Safety Event Reporting Procedures

9.2.1 Reporting Procedures for Disease-Related Events

The investigator is responsible for ensuring that all Disease-Related Events observed by the investigator or reported by the subject that occur after the first dose of investigational product through the end of study are recorded on the Event CRF as a Disease-Related Event.

Disease-Related Events assessed by the investigator to be more severe than expected and/or related to the investigational product(s)/study treatment/ protocol-required therapies, and determined to be serious, must be recorded on the Event CRF as Serious Adverse Events.

Additionally, the investigator is required to report a fatal Disease-Related Event on the Event CRF as a Disease-Related Event.

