10. STATISTICAL CONSIDERATIONS

10.1 Study Endpoints, Analysis Sets, and Covariates

10.1.1 Study Endpoints

[figure not shown]
Primary Endpoint:

- Safety: subject incidence and grade of adverse events and dose limiting toxicities (DLTs)

Secondary Endpoints:

- Pharmacokinetic parameters including, but not limited to: half-life, maximum observed concentration (C_{max}), minimum observed concentration (C_{min}), area under the concentration-time curve from time 0 to the time of the last quantifiable concentration (AUC_{0-last}) and clearance (CL) of AMG 673
- Efficacy parameters: response rate (response defined as CR/CRi/morphologic leukemia-free state [per modified IWG criteria] or CRh*), duration of response, time to progression, time to response

Exploratory Endpoints:

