10.4.2 Primary Endpoint

Safety Endpoints

Unless otherwise specified, statistical analyses on safety endpoints will be done using subjects from the safety analysis set, which includes subjects that are enrolled and received at least 1 dose of AMG 673.

Subject incidence of DLTs will be used to fit the BLRM model to estimate the probability of having a DLT across dose levels.

Adverse Events

Subject incidence of all treatment-emergent adverse events will be tabulated by system organ class and preferred term. The number and percentage of subjects reporting adverse events will be evaluated overall and by dose level and will also be tabulated by relationship to study drug.

Tables of disease-related events, fatal adverse events, serious adverse events, adverse events leading to withdrawal from investigational product or other protocol-required therapies, and significant treatment-emergent adverse events will also be provided.

Subject incidence of all disease-related events, fatal disease-related events, serious disease-related events, disease-related events leading to withdrawal from investigational product or other protocol-required therapies, and significant disease-related events will also be provided. Subject incidence of disease-related events and fatal disease-related events will be tabulated by system organ class and preferred term.

Subject incidence of first dose effects will be used to fit the BLRM model to estimate the probability of having an adverse event related to first dose effects across dose levels.

Clinical Laboratory Tests

Clinical chemistry, hematology, and urinalysis data will be listed and reviewed for each subject. Values outside the normal laboratory reference ranges will be flagged as high or low on the listings. Depending on the size and scope of changes in laboratory data, summaries of laboratory data over time and/or changes from baseline over time may be provided. Tables of maximum shifts from baseline for selected laboratory values may also be provided.

Vital Signs

Vital signs data will be listed and reviewed for each subject. Depending on the size and scope of changes, summaries of vital signs data over time and/or changes from baseline over time may be provided.

Electrocardiograms

Summaries over time and/or changes from baseline over time will be provided for all ECG parameters.

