**10. Changes From Protocol-specified Analyses**

**Time to Progression endpoint in protocol refers to Event Free Survival, to address the Relapse/refractory AML subjects who are already in progressive state and never respond.**

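### SAP section 5 counts disease-related events as TEAEs, which widens the AE part of the protocol's primary endpoint; SAP 9.6.2 does not mention them and SAP section 10 does not declare the change

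*SAP*

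**What the plan says.** **Protocol.** The primary endpoint in 10.1.1 is the incidence and grade of adverse events, together with DLTs. Disease-related events are not named in it.

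Section 9.1.1 sets up two classes. One is headed "Disease-Related Events that do not qualify as Adverse Events or Serious Adverse Events" and covers events in the normal course of the leukemia. The other covers events that are worse than expected, or where the investigator suspects that treatment caused the worsening; of these it says "this must be reported as an Adverse Event or Serious Adverse Event". Section 9.1.3 makes the same exception for seriousness: an adverse event meeting a serious criterion is an SAE "unless it meets the definition of a Disease-Related Event as defined in" Section 9.1.1. Under 9.2.1 disease-related events "are recorded on the Event CRF as a Disease-Related Event", so the database holds the category.

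Section 10.4.2 plans that "Subject incidence of all treatment-emergent adverse events will be tabulated by system organ class and preferred term", and then plans separate tables of disease-related events. The protocol gives no TEAE definition of its own.

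**SAP.** Section 5 defines TEAEs as adverse events "including disease related events", starting on or after first dose and up to end of study. SAP Appendix C shows that the phrase was a deliberate addition. Section 9.6.2 defines TEAEs again, as events with onset after first dose, and does not mention disease-related events. It also keeps separate disease-event tables. Section 10, which lists departures from the protocol, contains one entry: "Time to Progression endpoint in protocol refers to Event Free Survival".

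**The concern.** The TEAE tables report the adverse-event part of the primary endpoint. If section 5 is followed, they count subjects whose only event was one that the protocol says is not an adverse event. The number reported against the endpoint is then not the one the protocol describes, and the section meant to disclose such departures is silent on it.

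The two SAP definitions also differ, both on disease-related events and on whether an event starting on the first-dose day but not after the infusion counts. Two programmers working from the same SAP could build different primary tables.

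The overlap falls where it matters. The expected disease events in Protocol Appendix G include cytopenias, infections and haemorrhage, and Protocol Table 1 lists the same three as potential risks of AMG 673. In those rows, pooling mixes background leukemia events with the events in which one would look for a dose relation.

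**Working it through.** **1. The plan's own figures.** SAP 3.2 gives the probability of at least one adverse event among 10 expansion subjects as 65% at 10% incidence and 89% at 20%. With P = 1 − (1 − p)^10:

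- p = 0.10: 1 − 0.9^10 = 0.651
- p = 0.20: 1 − 0.8^10 = 0.893

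Both reproduce and are not in dispute.

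**2. Can AE-only incidence be recovered from the planned tables?** Let *a* be the proportion of subjects with an AE as the protocol defines it, *d* the proportion with an event recorded only as disease-related, and *u* the proportion with either. Whatever the overlap,

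max(a, d) ≤ u ≤ min(1, a + d).

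Knowing *u* and *d* therefore gives only u − d ≤ a ≤ u. As an illustration with assumed values, u = 96% and d = 90% leave *a* anywhere from 6% to 96%. The separate disease-event tables do not identify it.

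**3. How much could pooling dilute a dose contrast?** No document gives *d*, so it is assumed from 10% to 95%, equal at both doses and independent of AE occurrence. Then

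u = 1 − (1 − a)(1 − d),

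and a contrast between doses becomes (a₂ − a₁)(1 − d). The AE rates of 20% and 60% are also assumed, giving 0.40 × (1 − d):

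| Assumed d | Pooled, a = 20% | Pooled, a = 60% | Contrast (points) |
|---|---|---|---|
| 0% | 20% | 60% | 40 |
| 10% | 28% | 64% | 36 |
| 30% | 44% | 72% | 28 |
| 50% | 60% | 80% | 20 |
| 80% | 84% | 92% | 8 |
| 95% | 96% | 98% | 2 |

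Under these assumptions the contrast shrinks at every *d* above zero, but it nearly vanishes only when *d* is about 80% or more. Without independence, each pooled rate can lie anywhere within the bounds in step 2. At d = 30% and a = 20%, for example, it lies between 30% and 50%.

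**4. What the TEAE definition does not touch.** SAP section 5 takes DLTs from their own eCRF question, and SAP 9.6.1 fits the BLRM to DLT incidence. Neither uses the TEAE definition. Treatment-related AEs in SAP section 5 must be judged possibly caused by the product, so disease events judged unrelated drop out.

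**The case against.** Much of the case on the other side stands.

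- **The protocol's boundary is not perfectly clean.** It never defines TEAE. Its general AE definition in 9.1.2 requires no causal link, and that section discusses adverse events due to AML. Some disease-related events are AEs under 9.1.1 itself. Section 5 could even be read as meaning only those. In that case the added words are redundant and still need clarifying.
- **The SAP is inconsistent, not settled on pooling.** Section 9.6.2 lists AE tables and disease-event tables as separate families, which suggests that an AE-only table may be intended. The SAP does not say so.
- **The change is not hidden.** Appendix C records it. It is missing only from section 10.
- **Pooling has merit here.** In a single-arm first-in-human study, assigning a cytopenia or infection to disease or drug is a judgement. A table that ignores that judgement is the more inclusive safety display.

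A reader might infer that TEAE rates will sit near 100% at every dose. The documents do not support that: Appendix G is a broad list but carries no frequencies, and Protocol 9.2.2.4 says only that such events occur at some frequency. The AE rate matters too. If it were itself 95% (assumed), then with d = 90% pooling would give 1 − 0.05 × 0.10 = 99.5%, and the any-TEAE row would say little under either definition.

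A reader might also infer that pooling hides toxicity from dose decisions. It does not follow. Those decisions use DLTs through the BLRM and DLRT review of all available data, including grade 3 or higher toxicities that are not DLTs. Tables by preferred term limit the masking further: cytokine release syndrome, the identified risk in Protocol Table 1, is not in Appendix G.

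**Conclusion.** The mismatch is established from the text and needs no assumption. As written, section 5 yields an all-cause TEAE incidence wider than the AE component of the primary endpoint. The departure is undeclared in section 10, it conflicts with 9.6.2, and the AE-only figure cannot be worked back from the disease-event tables.

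The size is not established. The loss of 4 to 38 points from a 40-point contrast rests on assumed AE rates, an assumed disease-event rate of 10% to 95% that does not vary by dose, and independence. The DLT half of the primary endpoint and the DLT-based dose model are unaffected, and treatment-related AEs are largely protected by the causality filter. This is a minor point about definition and disclosure, worth correcting because the correction is cheap.

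**What to change.** - Use one TEAE definition in SAP sections 5 and 9.6.2, including a single rule for events on the day of first dose.
- Tabulate TEAEs excluding events recorded only as disease-related, which is the protocol's AE endpoint, side by side with the pooled table of AEs plus disease-related events. Show both by dose level, system organ class and preferred term.
- Declare the pooled definition in SAP section 10, with the reason for it.

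The cost is one extra table set, built from a category already on the Event CRF. No sample size, DLT analysis or stated probability changes. The AE-only table depends on investigators attributing events correctly between disease and drug, which is why the pooled table should be kept beside it.
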